8.3 Pregnancy Reporting

Participants who become pregnant during the study will be followed for safety. The investigator, or his/her qualified designee study center staff, will collect pregnancy information on any participant who becomes pregnant while participating in this study. The investigator or his/her qualified study center staff designee will record pregnancy information on the Pregnancy Report Form and submit it to the pharmacovigilance (PV) group at the study clinical research organization (CRO) within 24 hours of learning of a participant's pregnancy. The participant will be followed to determine the outcome of the pregnancy. At the end of the pregnancy, whether full-term or premature, information on the status of the mother and child will be forwarded to the Sponsor Safety Contact. Generally, follow-up will be no longer than 6 to 8 weeks following the estimated delivery date.

While pregnancy itself is not considered an AE/SAE, any pregnancy complication or elective termination of a pregnancy for medical reasons will be recorded as an AE or an SAE, and will be followed. A spontaneous abortion is always considered to be a SAE and will be reported. Furthermore, any SAE occurring as a result of a post-study pregnancy and considered reasonably related in time to receipt of the investigational product by the investigator, will be reported to the Sponsor Safety Contact. While the investigator is not obligated to actively seek this information from former study participants, he/she may learn of a pregnancy through spontaneous reporting. Information on pregnancies identified during the screening phase/prior to vaccine administration do not need to be collected; this information need not be communicated to the Sponsor.

The following events are considered SAEs related to pregnancy:

- spontaneous abortion (spontaneous pregnancy loss before 20 weeks gestation) or resulting in a fetus weighing less than 500 grams (Reproductive Care Program of Nova Scotia)
- ectopic and molar pregnancy
- stillbirth, defined as the complete expulsion or extraction from its mother after at least 20 weeks pregnancy, or after gaining a weight of 500 grams or more, of a fetus in which, after such expulsion or extraction, there is no breathing, beating of the heart, pulsation of the umbilical cord, or unmistakable movement of voluntary muscle.
- any early neonatal death (death of a liveborn infant within seven days of life)
- any congenital anomaly or birth defect identified in the offspring of a study participant at pregnancy, birth or later, regardless of whether fetus is alive or dead at birth

8.4 Detecting and Recording AEs and SAEs

Time period for detecting and recording adverse events and serious adverse events

All AEs starting after signing of the informed consent must be recorded into the appropriate section of the eCRF, irrespective of intensity or whether or not they are considered injection-related.

In order to avoid vague, ambiguous or colloquial expressions, the AE should be recorded in standard

medical terminology rather than the participant's own words. Whenever possible, the investigator should group together into a single term signs and symptoms which constitute a single diagnosis. Each AE is to be evaluated for duration, severity, seriousness and causal relationship to the investigational drug. The severity of the AE and its relationship to the test product will be assessed by the investigator. All participants who have an AE or SAE or have withdrawn early from the study due to an AE or SAE will be followed until resolution/stabilization as determined by the investigator or Sponsor or until the participant is lost to follow-up. All follow up data will be documented on the eCRF.

The time period for collecting and recording SAEs will begin at the first receipt of study vaccine/placebo and will end one year post first dose for each participant.

All AEs/SAEs leading to withdrawal from the study will be collected and recorded from the time of the first receipt of study vaccine/placebo. All SAEs will be collected and recorded from the time of the first receipt of study vaccine/placebo until the participant is discharged from the study.

In addition to the above-mentioned reporting requirements and in order to fulfill reporting obligations, SAEs that are related to study participation (i.e., protocol-mandated procedures, invasive tests, a change from existing therapy) will be collected and recorded from the time the participant consents to participate in the study until she/he is discharged from the study.

Post-Study adverse events and serious adverse events

A post-study AE/SAE is defined as any event that occurs outside of the AE/SAE reporting period (post Day 336). Investigators are not obligated to actively seek AEs or SAEs in former study participants. However, if the investigator learns of any SAE at any time after a participant has been discharged from the study, and he/she considers the event reasonably related to the investigational product/product, the investigator will promptly notify the PV Group at the study CRO or directly to the Sponsor in the event of study completion and study center closure.

8.5 Evaluation of Adverse Events and Serious Adverse Events

Active questioning to detect adverse events and serious adverse events

As a consistent method of collecting AEs, the participants should be asked a non-leading question such as:

'Have you acted differently or felt different in any way since receiving the product or since the last visit?'

When an AE/SAE occurs, it is the responsibility of the investigator to review all documentation (e.g., hospital progress notes, laboratory and diagnostics reports) relative to the event. The investigator will then record all relevant information regarding an AE/SAE in the eCRF and participant diary (and completed SAE/pregnancy reporting form if required) and send it to the PV Group at the study CRO.

The investigator will attempt to establish a diagnosis pertaining to the event based on signs, symptoms, laboratory tests, and/or other clinical information. In such cases, the diagnosis should be documented as the AE/SAE and not the individual signs/symptoms.

8.6 Assessment of Adverse Events

Each AE is to be evaluated for duration, severity (intensity), outcome, and causal relationship to the investigational drug.

The investigator will assess the maximum intensity that occurred over the duration of the event for all AEs (including SAEs) recorded during the study. The assessment will be based on participant reporting, the investigator's clinical judgment and FDA Guidance for industry (Toxicity grading scale for healthy adult and adolescent volunteers enrolled in preventive vaccine clinical studies, September 2007) and presented in [Table 5](#), [Table 6](#) and [Table 7](#).

The intensity of each sign or symptom reported will be graded using the 4-point severity scale shown in [Table 4](#).

Table 4: Severity Scale

Grade 1 (Mild)	No interference with daily activity
Grade 2 (Moderate)	Some interference with daily activity but not requiring medical intervention
Grade 3 (Severe)	Prevents daily activity and requires medical intervention
Grade 4 (Potentially life threatening)	Requiring Emergency Room (ER) visit or hospitalization

Table 5: Toxicity Grading Scale for Solicited Local Adverse Events

Solicited Local AE	Grade 1	Grade 2	Grade 3	Grade 4
Pain (pain without touching)	Does not interfere with activity	Repeated use of non-narcotic pain reliever >24 hours or interferes with activity	Any use of narcotic pain reliever or prevents daily activity	Emergency room (ER) visit or hospitalization
Tenderness (pain when area is touched)	Mild discomfort to touch	Discomfort with movement	Significant discomfort at rest	ER visit or hospitalization
Pruritus associated with injection See also skin: pruritus (itching - no skin lesions)	Itching localized to injection site AND relieved spontaneously or with <48 hours treatment	Itching beyond the injection site but not generalized OR Itching localized to injection site requiring ≥48 hours treatment	Generalized itching causing inability to perform usual social & functional activities	NA
Erythema/Redness ^a	2.5–5 cm	5.1–10 cm	>10 cm	Necrosis or exfoliative dermatitis
Induration/Swelling ^b	2.5–5 cm and does not interfere with activity	5.1–10 cm or interferes with activity	>10 cm or prevents daily activity	Necrosis

Abbreviations: AE=adverse event; NA=not applicable

^a In addition to grading the measured local reaction at the greatest single diameter, the measurement was recorded as a continuous variable.

^b Induration/Swelling was evaluated and graded using the functional scale as well as the actual measurement. Source: (US Food and Drug Administration 2007)

Table 6: Toxicity Grading Scale for Solicited Systemic Adverse Events

Systemic (General)	Mild (Grade 1)	Moderate (Grade 2)	Severe (Grade 3)	Potentially Life-Threatening (Grade 4)
Nausea/vomiting	No interference with activity or 1-2 episodes/24 hours	Some interference with activity or >2 episodes/24 hours	Prevents daily activity, requires outpatient IV hydration	ER visit or hospitalization for hypotensive shock
Diarrhea	2 - 3 loose stools or < 400 g/24 hours	4 - 5 stools or 400-800 g/24 hours	6 or more watery stools or >800 g/24 hours or requires outpatient IV hydration	ER visit or hospitalization
Headache	No interference with activity	Repeated use of non-narcotic pain reliever >24 hours or some interference with activity	Significant; any use of narcotic pain reliever or prevents daily activity	ER visit or hospitalization
Fatigue	No interference with activity	Some interference with activity	Significant; prevents daily activity	ER visit or hospitalization
Myalgia	No interference with activity	Some interference with activity	Significant; prevents daily activity	ER visit or hospitalization

Abbreviations: ER=emergency room; IV=intravenous Source: (US Food and Drug Administration 2007)

Table 7: Toxicity Grading Scale for Solicited Other Adverse Events

Vital Signs	Mild (Grade 1)	Moderate (Grade 2)	Severe (Grade 3)	Potentially Life-Threatening (Grade 4)
Fever ^a (°C) ** (°F) *	38.0–38.4 100.4–101.1	38.5–38.9 101.2–102.0	39.0–40 102.1–104	>40 >104
Tachycardia – beats/min	101–115	116–130	>130	ER visit or hospitalization for arrhythmia
Bradycardia – beats/min ^b	50–54	45–49	<45	ER visit or hospitalization for arrhythmia
Hypertension (systolic) - mm Hg	141–150	151–155	>155	ER visit or hospitalization for malignant hypertension
Hypertension (diastolic) - mm Hg	91–95	96–100	>100	ER visit or hospitalization for malignant hypertension
Hypotension (systolic) – mm Hg	85–89	80–84	<80	ER visit or hospitalization for hypotensive shock
Respiratory Rate – breaths/min	17–20	21–25	>25	Intubation

Abbreviations: ER=emergency room.

Note: Subject were at rest for all vital sign measurements

^aOral temperature; no recent hot or cold beverages or smoking

^bWhen resting heart rate was between 60-100 beats per minute. Clinical judgment was used when characterizing bradycardia among some healthy subject populations, eg, conditioned athletes Source: (US Food and Drug Administration 2007)

Assessment of causality

The investigator must make the determination of relationship to the study vaccine for each AE/SAE. Solicited local reactions are assumed to be related to study drug. The investigator should decide whether, in his/her medical judgment, there is a reasonable possibility that the event may have been caused by the investigational vaccine. If there is any valid reason, even if undetermined or untested, for suspecting a possible cause and effect relationship between the investigational vaccine and the occurrence of the AE,

then the AE should be considered “definitely”, “probably”, “possibly”, “unlikely”, or “unrelated”.

The investigator will review each event and assess its relationship to drug treatment using the criteria in [Table 9](#).

Table 8: FDA Guidance for Grading Clinical Laboratory Abnormalities

The laboratory values provided in the tables below serve as guidelines and are dependent upon institutional normal parameters. Institutional normal reference ranges should be provided to demonstrate that they are appropriate.

Conversion factors to SI units will be provided to the clinical sites.

Serum *	Mild (Grade 1)	Moderate (Grade 2)	Severe (Grade 3)	Potentially Life Threatening (Grade 4)**
Sodium – Hyponatremia mEq/L	132 – 134	130 – 131	125 – 129	< 125
Sodium – Hypernatremia mEq/L	144 – 145	146 – 147	148 – 150	> 150
Potassium – Hyperkalemia mEq/L	5.1 – 5.2	5.3 – 5.4	5.5 – 5.6	> 5.6
Potassium – Hypokalemia mEq/L	3.5 – 3.6	3.3 – 3.4	3.1 – 3.2	< 3.1
Glucose – Hypoglycemia mg/dL	65 – 69	55 – 64	45 – 54	< 45
Glucose – Hyperglycemia Fasting – mg/dL	100 – 110	111 – 12	>125	Insulin requirements or hyperosmolar coma
Random – mg/dL	110 – 125	126 – 200	>200	
Blood Urea Nitrogen BUN mg/dL	23 – 26	27 – 31	> 31	Requires dialysis
Creatinine – mg/dL	1.5 – 1.7	1.8 – 2.0	2.1 – 2.5	> 2.5 or requires dialysis

Serum *	Mild (Grade 1)	Moderate (Grade 2)	Severe (Grade 3)	Potentially Life Threatening (Grade 4)**
Calcium – hypocalcemia mg/dL	8.0 – 8.4	7.5 – 7.9	7.0 – 7.4	< 7.0
Calcium – hypercalcemia mg/dL	10.5 – 11.0	11.1 – 11.5	11.6 – 12.0	> 12.0
Magnesium – hypomagnesemia mg/dL	1.3 – 1.5	1.1 – 1.2	0.9 – 1.0	< 0.9
Phosphorous – hypophosphatemia mg/dL	2.3 – 2.5	2.0 – 2.2	1.6 – 1.9	< 1.6
CPK – mg/dL	1.25 – 1.5 x ULN***	1.6 – 3.0 x ULN	3.1 – 10 x ULN	> 10 x ULN
Albumin – Hypoalbuminemia g/dL	2.8 – 3.1	2.5 – 2.7	< 2.5	--
Total Protein – Hypoproteinemia g/dL	5.5 – 6.0	5.0 – 5.4	< 5.0	--
Alkaline phosphate – increase by factor	1.1 – 2.0 x ULN	2.1 – 3.0 x ULN	3.1 – 10 x ULN	> 10 x ULN
Liver Function Tests –ALT, AST increase by factor	1.1 – 2.5 x ULN	2.6 – 5.0 x ULN	5.1 – 10 x ULN	> 10 x ULN
Bilirubin – when accompanied by any increase in Liver Function Test increase by factor	1.1 – 1.25 x ULN	1.26 – 1.5 x ULN	1.51 – 1.75 x ULN	> 1.75 x ULN
Bilirubin – when Liver Function Test is normal; increase by factor	1.1 – 1.5 x ULN	1.6 – 2.0 x ULN	2.0 – 3.0 x ULN	> 3.0 x ULN
Cholesterol	201 – 210	211 – 225	> 226	---
Pancreatic enzymes – amylase, lipase	1.1 – 1.5 x ULN	1.6 – 2.0 x ULN	2.1 – 5.0 x ULN	> 5.0 x ULN

* The laboratory values provided in the tables serve as guidelines and are dependent upon institutional normal parameters. Institutional normal reference ranges should be provided to demonstrate that they are appropriate. ** The clinical signs or symptoms associated with laboratory abnormalities might result in characterization of the laboratory abnormalities as Potentially Life Threatening (Grade 4). For example, a low sodium value that falls within a grade 3 parameter (125-129 mEq/L) should be recorded as a grade 4 hyponatremia event if the subject had a new seizure associated with the low sodium value.

***ULN is the upper limit of the normal range.

Hematology *	Mild (Grade 1)	Moderate (Grade 2)	Severe (Grade 3)	Potentially Life Threatening (Grade 4)
Hemoglobin (Female) - gm/dL	11.0 – 12.0	9.5 – 10.9	8.0 – 9.4	< 8.0
Hemoglobin (Female) change from baseline value - gm/dL	Any decrease – 1.5	1.6 – 2.0	2.1 – 5.0	> 5.0
Hemoglobin (Male) - gm/dL	12.5 – 13.5	10.5 – 12.4	8.5 – 10.4	< 8.5
Hemoglobin (Male) change from baseline value – gm/dL	Any decrease – 1.5	1.6 – 2.0	2.1 – 5.0	> 5.0
WBC Increase - cell/mm ³	10,800 – 15,000	15,001 – 20,000	20,001 – 25,000	> 25,000
WBC Decrease - cell/mm ³	2,500 – 3,500	1,500 – 2,499	1,000 – 1,499	< 1,000
Lymphocytes Decrease - cell/mm ³	750 – 1,000	500 – 749	250 – 499	< 250
Neutrophils Decrease - cell/mm ³	1,500 – 2,000	1,000 – 1,499	500 – 999	< 500
Eosinophils - cell/mm ³	650 – 1500	1501 - 5000	> 5000	Hypereosinophilic
Platelets Decreased - cell/mm ³	125,000 – 140,000	100,000 – 124,000	25,000 – 99,000	< 25,000
PT – increase by factor (prothrombin time)	1.0 – 1.10 x ULN**	1.11 – 1.20 x ULN	1.21 – 1.25 x ULN	> 1.25 ULN

Hematology *	Mild (Grade 1)	Moderate (Grade 2)	Severe (Grade 3)	Potentially Life Threatening (Grade 4)
PTT – increase by factor (partial thromboplastin time)	1.0 – 1.2 x ULN	1.21 – 1.4 x ULN	1.41 – 1.5 x ULN	> 1.5 x ULN
Fibrinogen increase - mg/dL	400 – 500	501 – 600	> 600	--
Fibrinogen decrease - mg/dL	150 – 200	125 – 149	100 – 124	< 100 or associated with gross bleeding or disseminated intravascular coagulation (DIC)

*The laboratory values provided in the tables serve as guidelines and are dependent upon institutional normal parameters. Institutional normal reference ranges should be provided to demonstrate that they are appropriate.

** "ULN" is the upper limit of the normal range.

Urine *	Mild (Grade 1)	Moderate (Grade 2)	Severe (Grade 3)	Potentially Life Threatening (Grade 4)
Protein	Trace	1+	2+	Hospitalization or dialysis
Glucose	Trace	1+	2+	Hospitalization for hyperglycemia
Blood (microscopic) – red blood cells per high power field (rbc/hpf)	1 - 10	11 – 50	> 50 and/or gross blood	Hospitalization or packed red blood cells (PRBC) transfusion

*The laboratory values provided in the tables serve as guidelines and are dependent upon institutional normal parameters. Institutional normal reference ranges should be provided to demonstrate that they are appropriate.

Table 9: Assessment Criteria

Term	Assessment Criteria	Description
Definitely	
 Event or laboratory test abnormality, with plausible time relationship to drug intake Cannot be explained by disease or other drugs Response to withdrawal plausible (pharmacologically, pathologically) Event definitive pharmacologically or phenomenologically (i.e., an objective and specific medical disorder or a recognized pharmacological phenomenon) Re-challenge (response to drug re-administration) satisfactory, if necessary 	A clinical event, including laboratory test abnormality, occurring in a plausible time relationship to drug administration, and which cannot be explained by concurrent disease or other drugs or chemicals. The response to withdrawal of the drug (de-challenge) should be clinically plausible. The event must be definitive pharmacologically or phenomenologically, using a satisfactory re-challenge procedure if necessary.

Term	Assessment Criteria	Description
Probably	
 Event or laboratory test abnormality, with reasonable time relationship to drug intake Unlikely to be attributed to disease or other drugs Response to withdrawal clinically reasonable Re-challenge not required 	A clinical event, including laboratory test abnormality, with a reasonable time sequence to administration of the drug, unlikely to be attributed to concurrent disease or other drugs or chemicals, and which follows a clinically reasonable response on withdrawal (de-challenge). Re-challenge information is not required to fulfil this definition.
Possibly	
 Event or laboratory test abnormality, with reasonable time relationship to drug intake Could also be explained by disease or other drugs Information on drug withdrawal may be lacking or unclear 	A clinical event, including laboratory test abnormality, with a reasonable time sequence to administration of the drug, but which could also be explained by concurrent disease or other drugs or chemicals. Information on drug withdrawal may be lacking or unclear.
Unlikely	
 Event or laboratory test abnormality, with a time to drug intake that makes a relationship improbable (but not impossible) Disease or other drugs provide plausible explanations 	A clinical event, including laboratory test abnormality, with a temporal relationship to drug administration which makes a causal relationship improbable, and in which other drugs, chemicals or underlying disease provide plausible explanations.
Unrelated	
 The adverse event is clearly not related to the investigational agent/procedure. 	Another cause of the event is most plausible; and/or a clinically plausible temporal sequence is inconsistent with the onset of the event and the study intervention and/or a causal relationship is considered biologically implausible.

Assessment of outcomes

The investigator will assess the outcome of all AEs (including SAEs) recorded during the study as:

- Ongoing
- Recovered/resolved
- Recovered/Resolved with sequelae
- Recovering/Improving
- Stabilized
- Unknown/Lost to Follow-up
- Fatal (SAE)

Medically attended visits

For each symptom the participant experiences, the participant will be asked if the participant received medical attention defined as hospitalization, or an otherwise unscheduled visit to or from medical personnel for any reason, including emergency room visits. This information will be recorded in the eCRF.

8.7 Reporting of Serious Adverse Events and Other Events

The Sponsor has a legal responsibility to promptly notify appropriate regulatory agencies about the safety of a product under clinical investigation. Prompt notification of SAEs by the investigator to the Study Contact for Reporting SAEs is essential so that legal obligations and ethical responsibilities towards the safety of other participants are met. The purpose of the report is to fulfill specific regulatory and GCP requirements, regarding the product under investigation. All of these notifications will occur within 24 hours of the investigator becoming aware of the SAE.

For reporting of a SAE or pregnancy, the investigator shall use the designated SAE or pregnancy report form. Occurrence of any SAE/pregnancy must be reported immediately (within one working day) once the investigative study center has knowledge of the event.

If an SAE or pregnancy occurs to a participant during this study, the SAE report and relevant medical records should be sent (within 24 hours) to the contact listed below ([Table 10](#)).

Table 10: Timeframes for Submitting Serious Adverse Event and Other Event Reports

Type of Event	Initial Reports		Follow-up of Relevant Information on a Previous Report	
	Timeframe	Documents	Timeframe	Documents
SAEs	24 hours*	SAE report	24 hours*	SAE report
Pregnancy	24 hours**	Pregnancy report form	24 hours*	Pregnancy report form

*Timeframe allowed after receipt or awareness of the information.

**Timeframe allowed after the diagnosis is established and known to the investigator

Contact information for reporting serious adverse events

[name], PhD

Chief Medical Officer, VBI Vaccines Inc. [contact]

Email: [contact]

Completion and transmission of SAE reports

Once an investigator becomes aware that a SAE/ pregnancy has occurred in a study participant, the investigator (or qualified study center designee) must complete the information in the SAE/pregnancy report as thoroughly as possible with all available details of the event, **WITHIN 24 HOURS**. Even if the investigator does not have all information regarding a SAE, the report should still be completed within 24 hours and be appropriately documented in the eCRF. Once additional relevant information is received, the report should be updated **WITHIN 24 HOURS**.

8.7.1 Unblinding

Blinding will be guaranteed by the preparation of the study vaccine by an unblinded pharmacist or other qualified study-site personnel with primary responsibility for study vaccine preparation.

Participants will be randomly assigned to groups based on a computer-generated randomization schedule prepared before the study by or under the supervision of the sponsor and using the IWRS.

The investigator will not be provided with randomization codes. The codes will be maintained within the IWRS, which has the functionality to allow the investigator to break the blind for an individual participant.

Data that may potentially unblind the study vaccine assignment (e.g., immunogenicity data, study vaccine accountability data, study vaccine allocation, biomarker, or other specific laboratory data) will be handled with special care to ensure that the integrity of the blind is maintained and the potential for bias is minimized. This can include making special provisions, such as segregating the data in question from view by the investigators, clinical team, or others as appropriate until the time of database lock and unblinding.

Each phase of the study will be unblinded after DSMB review of safety data collected through Day 56. Some key personnel of the sponsor, not involved in study operations, may be unblinded at the time of Study Steering Committee analysis. The investigator may in an emergency determine the identity of the intervention by contacting the IWRS. While the responsibility to break the intervention code in emergency situations resides solely with the investigator, it is recommended that the investigator contact the sponsor or its designee if possible, to discuss the particular situation, before breaking the blind.

Telephone contact with the sponsor or its designee will be available 24 hours per day, 7 days per week. In the event the blind is broken, the sponsor must be informed as soon as possible. The date, time, and reason for the unblinding must be documented in the IWRS and in the source document. The documentation received from the IWRS indicating the code break must be retained with the participant's source documents in a secure manner.

Participants who have had their intervention assignment unblinded should continue to return for scheduled evaluations. Participants should not be allowed to receive further study vaccinations and are only to be followed for safety evaluation visits.

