The immunogenicity population will include all participants who receive the prescribed study vaccine or placebo and underwent at least one immunogenicity assessment after vaccination.

The Study Steering Committee (SSC), comprised of representatives from the study sponsor (not involved in study operations) and external vaccine experts, will review unblinded immunogenicity data 7 days and 28 days after the first vaccinations (Phase 1a and Phase 1b)). The study will be unblinded following DSMB review of safety data collected through Day 56. Study participants will continue with study visits as planned up to 12 months of follow up after the first dose of study vaccine.

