7.11 Contraindications to Administration of the Product

The following events constitute contraindications to administration of the study products at that point in time; if any of these events occur at the time scheduled for injection, the participant may be injected at a later date, within the time window specified in the protocol (+/-3 days for Day 28 administration), or withdrawn at the discretion of the investigator.

Acute disease and/or fever at the time of administration. Fever is defined as temperature $\geq 38.0^{\circ}\text{C} / 100.4^{\circ}\text{F}$ oral.

Participants with any signs or symptoms consistent with COVID-19 illness (as described in the [Section 4.2](#)) should not receive the study vaccine.

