9.2 Study Vaccine Discontinuation

In rare instances, it may be necessary for a participant to permanently discontinue study vaccination. Reasons for vaccine discontinuation may include the following:

- Non-serious AE / SAE
- Positive SARS-CoV-2 (PCR or rapid antigen test)
- Participant request
- Investigator request
- Pregnancy
- Protocol deviation (including no longer meeting all the inclusion criteria, or meeting 1 or more exclusion criteria)
- Other (specify)

Note that discontinuation of study intervention does not represent withdrawal from the study. If study vaccination is permanently discontinued, the participant will remain in the study to be evaluated for safety, immunogenicity, and efficacy.

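### The closing sentence of Protocol 8.7.1 restricts individually unblinded participants to safety visits, against the sentence before it and, for Phase 1a code breaks before Day 28, against section 9.2

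*Protocol*

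**What the plan says.** Protocol 8.7.1 covers two kinds of unblinding. One is planned and applies to everyone: "Each phase of the study will be unblinded after DSMB review of safety data collected through Day 56". The other is individual: "The investigator may in an emergency determine the identity of the intervention by contacting the IWRS". The section then sets out how a code break is reported and documented, and closes with two sentences on what happens next. The first is "Participants who have had their intervention assignment unblinded should continue to return for scheduled evaluations". The second is "Participants should not be allowed to receive further study vaccinations and are only to be followed for safety evaluation visits". Neither sentence says which kind of unblinding it covers.

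Protocol 9.2, on stopping study vaccination, says: "If study vaccination is permanently discontinued, the participant will remain in the study to be evaluated for safety, immunogenicity, and efficacy". Its list of reasons does not name unblinding, but it includes adverse events and an open category for other reasons.

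Protocol 4.13 mentions the Day 56 unblinding and continues: "Study participants will continue with study visits as planned up to 12 months of follow up after the first dose of study vaccine". The synopsis (Study Design, Phase 1a) and section 4.1 (Phase 1b) say the same.

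SAP 4.4 and 4.5 censor immunogenicity data after three events: a non-study COVID-19 vaccine, a positive SARS-CoV-2 test, or onset of COVID-19 illness. Unblinding is not among them.

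**The concern.** A site that breaks the code for one participant needs to know whether to go on drawing titer samples. The closing sentence of 8.7.1 says no. The sentence before it and, where a dose is still due, section 9.2 say yes.

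The missing titers would not be a random subset. The code break is for emergencies, and section 10.7.1 lets the DSMB ask for unblinding when a case needs further safety assessment. The people affected are therefore likely to be selected by safety events. If reactogenicity and antibody response are related, the remaining titers describe a selected group. The SAP could not repair this: section 5.4 imputes no missing data unless otherwise specified, and the censoring rules give no reason for these samples to be absent.

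**Working it through.** The plan states no figure on this point, so the check compares the texts and counts visits.

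**1. Which rules apply to an individually unblinded participant**

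- Phase 1a, code broken after dose 1 and before Day 28. A dose is still due (injection visits are Days 1 and 28, section 6.1.6). Section 8.7.1 bars it, which amounts to permanent discontinuation, so 9.2 applies and requires immunogenicity follow-up. The closing sentence of 8.7.1 limits follow-up to safety. This is a direct conflict between sections, on top of the one inside 8.7.1.
- Phase 1a, code broken after Day 28. No dose remains, so 9.2 is not triggered. The conflict is between the two closing sentences of 8.7.1.
- Phase 1b, code broken after Day 1. There is only one dose, so again 9.2 is not triggered and the conflict lies within 8.7.1. The vaccination clause has nothing left to act on, and the practical effect of the rule is to stop titers.

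**2. Titer samples at stake for one participant**

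Post-baseline titer days (sections 6.1.12 and 10.1.2) are 7, 28, 35, 56, 112, 224 and 336 in Phase 1a, and 7, 14, 28, 56, 84, 168 and 336 in Phase 1b: seven in each.

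- Code broken before the Day 7 sample: all 7 are lost. The FAS requires an evaluable sample both at baseline and afterwards (SAP 4.4), so this participant leaves the FAS altogether.
- Phase 1a, code broken between the Day 7 and Day 28 samples: 7 − 1 = 6 are lost, including Days 28 and 56, which section 4.4 uses as the primary determinant for immunogenicity.

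Apart from related SAEs, the individual stopping events in section 10.7 are those within 7 days of injection, so an early code break is plausible.

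**3. Share of a group**

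- Phase 1a: 1/20 = 5% of the group at each later visit.
- Phase 1b: 1/27 = 3.7%.

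These are shares per participant. The documents give no expected number of code breaks, so no total follows.

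**4. Which analysis sets are touched**

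The SAP's PPC requires all study vaccinations according to the protocol (SAP 4.5). A Phase 1a participant unblinded before Day 28 would therefore be outside the PPC anyway, and the loss falls on the FAS. In Phase 1b the single dose has already been given, so the loss can reach both sets.

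**The case against.** A reader might infer that, because every participant is unblinded after Day 56, the closing sentence ends titer sampling for the whole trial from then on. That would remove 3 of the 7 post-baseline titer visits in each phase (Days 112, 224 and 336; Days 84, 168 and 336). The documents do not support this reading. The rule closes the text on the emergency code break. Its bar on vaccination would be empty after Day 56, since no injection is scheduled then. The synopsis, 4.1 and 4.13 each say that visits continue as planned after the Day 56 unblinding, and the SAP acknowledges that unblinding (section 7) while keeping the late time points (section 6.4.2).

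A reader might also bring in section 7.11, where a participant may be "or withdrawn at the discretion of the investigator". That provision concerns acute illness, fever or COVID-19 symptoms at the time of injection. It does not deal with unblinding and is not part of this point.

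The two closing sentences of 8.7.1 can be reconciled: participants attend on the scheduled days, but only for the safety content. That softens the clash inside the section, but it confirms the loss of titers and leaves the conflict with 9.2 in place.

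Finally, the effect may be small. Immunogenicity is secondary and presented descriptively, section 10.3 calls it exploratory, code breaks may be few or none, and informative loss is plausible rather than shown. All of this stands. It limits the weight of the point but does not tell a site which instruction to follow.

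**Conclusion.** The point holds in a narrow form. The closing sentence of 8.7.1 contradicts the sentence before it as ordinarily read. For a Phase 1a participant whose code is broken between Days 1 and 28, it also contradicts 9.2. Followed as written, it would end titer sampling that is already scheduled and that the SAP does not exclude.

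The size is 5% of a Phase 1a group or 3.7% of a Phase 1b group per participant, over up to seven visits, with the number of participants unknown. The late titer endpoints are not invalidated.

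The conclusion rests on two assumptions: that individual code breaks arise mainly from safety events, which the emergency and DSMB provisions suggest but do not quantify, and that a participant barred from further vaccination by 8.7.1 counts as permanently discontinued under 9.2.

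**What to change.** Reconcile 8.7.1 with 9.2:

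- State that the closing rule applies to individual code breaks.
- Replace the restriction to safety visits with continuation of all scheduled safety and immunogenicity evaluations.
- Add a cross-reference to 4.13 for follow-up after the planned Day 56 unblinding.

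The part of the rule on further vaccination is not addressed here.

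The cost is a sentence or two of protocol wording. The visits and blood draws are already in the schedule, and the SAP's censoring rules need no change.
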